6.6.2 Health-related Quality of Life

Quality of life will be assessed by means of the Dermatology Life Quality Index (DLQI), a validated, 10-item general dermatology disability index designed to assess health-related quality of life in adult subjects with skin diseases such as eczema, psoriasis, acne, and viral warts (Finlay AY et al. 1994). The measure is self-administered and includes domains of daily activities, leisure, personal relationships, symptoms and feelings, treatment, and work/school activities. The DLQI has well-established reliability and validity as determined in several studies (Shikiar et al 2003, Badia X et al. 1999, Lewis V et al. 2004, Shikiar et al. 2006).

Moreover, it is frequently used in clinical psoriasis trials, has been tested across 32 different skin conditions and is available in 55 languages. The recall period is the previous week, and the instrument requires 1 to 2 minutes to complete. Each item has four response categories ranging from 0 (not at all) to 3 (very much). “Not relevant” is also a valid response and is scored as 0. The DLQI[©] total score is a sum of the 10 questions. Scores range from 0 to 30 and higher scores indicate greater health-related quality of life impairment. Each subscale of the DLQI[©] may be analyzed separately.

Patients will be asked to complete the questionnaire at visits 3, 10 and 12 of the core study and at visits 2 and 4 of the extension period.

Completed questionnaires will be reviewed and examined by the investigator before the clinical examination for responses that may indicate potential AEs or SAEs. The investigator should review not only the responses to the questions in the questionnaires but also any unsolicited comments written by the patient.

If the occurrence of AEs or SAEs is confirmed, the physician must record the events as per instructions given in [Section 7.2](#) of the protocol.

[figure not shown]

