2.1.1 General definitions

2.1.1.1 Study treatment: Study treatment refers to:

Secukinumab 300 mg (two s.c. injections of secukinumab 150 mg).

2.1.1.2 Study treatment start and end date:

Study treatment start date is defined as the first date when a non-zero dose of study drug is administered and recorded on the Dose Administration Record (DAR) CRF page. Similarly, study drug end date is defined as the last date when a non-zero dose of study drug is administered and recorded on the DAR CRF page.

2.1.1.3 Study day:

Study day will be calculated as (event date – study drug start date + 1 day) for events that occurred on or after study drug start date (e.g.visit, lab samples, AEs). For events prior to study drug start date (e.g., an adverse event occurred before the start of first dose), study day will be negative and calculated as (event date – study drug start date). Note that study drug start date is study day 1 and the day before study drug start date is study day -1 (i.e. no study day 0).

Due to the study drug dosing schedule, one month will be considered as 28 days. Time from events prior to the start of study drug, e.g., time since diagnosis, is calculated as the difference between the start date of study drug and the date of prior event.

Note that, the first dose day is Day 1, and the day before the first dose day is counted as Day - 1 (not Day 0).

2.1.1.4 Baseline and post baseline:

In general, a *baseline* value refers to measurement corresponding to week 0 assessment. A post-baseline value refers to a measurement taken after week 0 assessment.

Change from baseline will only be summarized for patients with both baseline and postbaseline unless stated otherwise, and it will be calculated as:

post-baseline value – baseline value

Correspondingly, percentage change will be calculated as:

100 * (post-baseline value – baseline value) / baseline value

For DLQI, In case baseline value is zero (0), percentage change will be calculated as (post-baseline value -0)*100 %.

2.1.1.5 Study periods:

The study has four periods: a screening period consisting of two visits (pre-screening and screening), an induction period of 4 weeks, a maintenance period of 20 weeks and an extension period of 48 weeks.

For analyses which will be done by phases (i.e., Core and Extension separately) the following rules will be applied to summarize the data.

For spontaneous data (CM, AE) as below:

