For parameters which are not collected at every visit (e.g. DLQI, HADS, **1999**), visit windows defined in Table 2.1 will be combined. For example, if a parameter is measured at Week 16 and Week 24 only, Week 16 visit window will extend from Day 2 to Day 126 (combining Week 1 to Week 16 visit windows), Week 24 will extend from Day 127 to Day 210 (combining Week 20 to Week 24 visit windows). Similarly, in extension phase, if a parameter is measured at E2 and E4 only, E2 window will extend from E0 to (A(E0) +43+2*83) (combining E0 to E2 visit windows).

For any assessments which are only in Core phase, and if any results are mapped to extension phase analyses visits, then such records will not be displayed at extension.

If more than one assessment falls into the interval, the rules defined in Section 2.1.1.7 below are applied.

The analysis visit will be used for listing of visit and period for safety data.

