2.2 Analysis sets

The following analysis populations will be defined for statistical analysis.

- All patients: all patients who signed informed consent and entered in the study, including screen failure.
- Full Analysis Set (FAS): all enrolled patients (i.e. patients entered at week 0 visit 3).
- Safety: all enrolled patients included in the FAS population who were given at least one dose of study drug.
- Intent-to-treat (ITT): all patients included in the safety population with at least one post-baseline efficacy assessment and with the Cw6 assessment.
- Per-Protocol (PP): all patients included in the ITT population who completed the study without any major protocol violation.
- Core phase completers set: All patients who completed the Core phase visits (Week 24) are called core phase completer set.

The primary and secondary objectives will be evaluated on the ITT population. A supportive analysis will be done on the PP population.

All safety evaluations will be based on the safety set.

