2.5.3 Handling of missing values/censoring/discontinuations

For patients who prematurely discontinue the study for any reason or patients with missing visits (after baseline), PASI will be imputed using the Last Observation Carried Forward (LOCF) approach. Additionaly non-responder imputation (NRI) analysis will be performed on primary endpoint (i.e., PASI 90 response with logistic regression analysis).

Non-responder imputation rule:

Non-responder imputation will be used: Missing values with respect to response variables based on PASI score will be imputed with non-response regardless to the reason for missing data (e.g. premature study discontinuation, missed visit, administrative issues), exceptions will apply to the following:

• If a subject dropped out the study prior to last scheduled visit and being responders consecutively at least for two preceding visits, the subject will be imputed as responder for the last scheduled visit.

• If a subject who was responder at visit x-1 and visit x+1 but has missing data at visit x, then the subject will be imputed for visit x.

The approach describes above will be adopted also for PASI 90 assessement reported in the extension phase.

The LOCF approach, as well as the NRI approach will be performed for drop-outs and patients with missing visits in between, however no imputation will be done on any visits for patients – entered in the extension phase **and** who have completed the study before reaching 72 weeks.

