2.11 Patient-reported outcomes

Variables related to health-related quality of life (HR-QoL) are described below. All HR-QoL variables will be evaluated based on Safety set. Both prevalence and LOCF approach will be adopted.

Dermatology Life Quality Index

Seven scores will be derived from the DLQI: the total score of each of the six dimensions as well as the total score over all items. The higher the score, the more quality of life is impaired.

The percentage change from baseline will be derived for each of the seven scores. Summary statistics will be provided for absolute values as well as for the percentage change by visit.

Changes from baseline in DLQI at each time point will be analyzed by means of a paired ttest or Wilcoxon signed-rank test, based on data distribution.

In addition, summary statistics will be provided for the number of patients achieving DLQI 0 or 1 at each time point specifying absolute and relative frequency of patients with DLQI 0/1 response. Further, comparison between baseline and each time point for proportion of patients achieving DLQI 0 or 1 will be performed using McNemar's test.

Following details to the DLQI scoring: The scoring of each question is as follows

- Very much: scored 3
- A lot: scored 2
- A little: scored 1

- Not at all: scored 0
- Not relevant: scored 0
- Question unanswered: scored 0
- Question 7: "prevented work or studying": scored 3

The DLQI total score will be calculated by summing the score of each question resulting in a maximum of 30 and a minimum of 0. The highger the score, the more quality of life is impaired.

Meaning of DLQI scores:

- 0-1= no effect at all on patient's life
- 2-5= small effect on patient's life
- 6-10= moderate effect on patient's life
- 11-20= very large effect on patient's life
- 21-30= extremely large effect on patient's life

The DLQI will be analyzed under six headings as follows:

- Symptoms and feelings: questions 1 and 2, score maximum 6
- Daily activities: questions 3 and 4, score maximum 6
- Leisure: questions 5 and 6, score maximum 6
- Work and school: question 7, score maximum 3
- Personal relationships: question 8 and 9, score maximum 6
- Treatment: question 10, score maximum 3

Interpretation of incorrectly completed questinnaires:

There is very high success rate of accurate completion of the DLQI. However, sometimes patients do make mistakes.

- 1. If one question is left unanswered this is scored as 0.

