2.14 Interim analysis

No interim analysis is planned for this study.

3 Sample size calculation

The primary objective of this study is to evaluate the clinical response in PASI 90 at week 16 of Cw6-negative and Cw6-positive psoriatic patients. According to literature data, Cw6-positive patients will be about 60% of the entire psoriatic patient population.

From a previous study with ustekinumab (Talamonti et al. 2013) we can observe a difference in response to PASI 90 between Cw6-positive vs Cw6-negative patients of around 30%, in favor of Cw6-POS. Therefore, it is sensible to expect a response in the Cw6-negative cohort not less than 12 % respect to the Cw6-positive group. Further considerations are stated in the paragraph below.

Phase III data on secukinumab show a PASI 90 response at 16 weeks of 71%. Under the assumption that 60% of all the enrolled patient population is represented by Cw6-POS patients, we can reasonably assume to observe a proportion of patients with PASI 90 of 80% in the Cw6-POS cohort.

Under these assumptions, considering a one-side alpha level of 0.025 and a power of 80%, 365 patients (219 Cw6-POS and 146 Cw6-NEG) are sufficient to evaluate if the response in terms of PASI 90 in the Cw6-negative cohort is not less than 12% respect to the Cw6-positive cohort.

Considering a dropout rate at 16 weeks of 10% equally divided in the two studied cohorts, a total of 406 patients should be enrolled.

All calculations were done with NQuery 7.0.

A power analysis based on a different Cw6 patient distribution was made in order to facilitate patient enrollment without power-loss in the primary endpoint evaluation. Table 3-1 shows how the enrollment rate should be set free until the ratio between Cw6-POS and Cw6-NEG reaches the 1:1 rate-distribution, with a power of at least 80%.

In particular, the number of Cw6-POS evaluable patients will range from 219 to 182, whereas those in the Cw6-NEG cohort will range from 146 to 182.

Based on the table below, the enrollment in one of the two cohorts will be stopped when the target number is achieved (a maximum of 244 Cw6-POS patients will be allowed).

Table 3-1:Power analysis

Power	Ratio	Cw6	Cw6	Cw6	Cw6	Overall	Cw6	Cw6	

For business use only

		POS	POS	POS	POS		POS	POS
		%	%	Ν	Ν	Ν	%	%
80%	0.66	60%	40%	219	146	365	244	163
80%	0.70	59%	41%	215	150	365	239	167
80%	0.72	58%	42%	212	153	365	236	170
80%	0.75	57%	43%	209	156	365	233	174
81%	0.79	56%	44%	204	161	365	227	179

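### Unless baseline is carried forward, the week-16 LOCF analysis of DLQI and HADS change repeats the observed-data analysis, and patients who left earlier without a questionnaire are in neither

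*SAP*

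**What the plan says.** On missing data for patient-reported outcomes, SAP 2.11 has one line: "All HR-QoL variables will be evaluated based on Safety set. Both prevalence and LOCF approach will be adopted". Prevalence is the SAP's term for observed data. Changes are tested with a paired t-test or Wilcoxon signed-rank test, and DLQI 0/1 against baseline with McNemar's test. The section states neither a baseline carry-forward rule nor a denominator for DLQI 0/1.

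Three other places matter:

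- **Schedule.** Protocol 6.6.2 says of the DLQI: "Patients will be asked to complete the questionnaire at visits 3, 10 and 12 of the core study". Protocol 6.6.3 gives HADS the same schedule. Table 6-1 places these visits at weeks 0, 16 and 24. The extension adds weeks 48 and 72.
- **Window.** SAP 2.1.1.6 names DLQI and HADS among the parameters with merged windows: "if a parameter is measured at Week 16 and Week 24 only, Week 16 visit window will extend from Day 2 to Day 126".
- **Change scores.** SAP 2.1.1.4: "Change from baseline will only be summarized for patients with both baseline and postbaseline unless stated otherwise".

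For PASI the SAP does more. Section 2.5.3 adds non-responder imputation: "Missing values with respect to response variables based on PASI score will be imputed with non-response", with stated exceptions. Section 2.7.2 extends non-responder imputation to IGA 0/1 and plans MMRM and multiple imputation for PASI change. None of this is carried over to DLQI or HADS. On the analysis set, SAP 2.2 says: "The primary and secondary objectives will be evaluated on the ITT population", whereas 2.11 uses the Safety set.

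**The concern.** Two approaches side by side suggest that the second tests how far the first depends on missing data. At week 16, the first post-baseline time point for these scales, it may test nothing. If both omit the same patients, agreement between them is automatic and gives no reassurance.

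DLQI and HADS are secondary objectives framed for the whole study population. A patient who leaves at week 8 without a questionnaire counts as a PASI 90 failure at week 16 under non-responder imputation, but drops out of the quality-of-life change analysis at the same visit. If such patients did worse than those who stayed, mean improvement, and possibly the DLQI 0/1 rate, would look better than they should, and the planned pair of analyses could not show it. SAP 2.7.2 itself remarks, about PASI, that observed data tend to overestimate within-group change.

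**Working it through.** **Inputs.** Schedule: weeks 0, 16, 24 (Protocol 6.6.2, 6.6.3, Table 6-1). Week-16 window: Day 2 to 126 (SAP 2.1.1.6). Dropout by week 16: 10% (Protocol 9.7, SAP 3). The documents give no expected DLQI or HADS result, so the DLQI 0/1 rates below are assumptions.

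**The plan's own figure.** 365 / 0.90 = 405.6, rounded up to 406, as stated. The allowance is 406 − 365 = 41 patients, or 41/406 = 10.1%.

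**What LOCF can carry to week 16.** A carried value must come from before the window. The window starts on Day 2, so any post-baseline questionnaire up to Day 126 is already the observed week-16 value. Only baseline remains.

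- Baseline not carried (the SAP 2.1.1.4 default for change): LOCF equals observed data for every patient, and the paired tests use the same pairs.
- Baseline carried: the analyses differ, but 2.11 does not state this rule.

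Invented data for 406 patients, with 41 leavers and 10 missed week-16 questionnaires, show this:

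| Week-16 analysis | Patients | Mean DLQI change | DLQI 0/1 among those with a value |
|---|---|---|---|
| Observed | 355 | −8.4 | 34.4% |
| LOCF, baseline not carried | 355 | −8.4 | 34.4% |
| LOCF, baseline carried | 406 | −7.3 | 30.3% |

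**Later visits.** Week-16 values can be carried to week 24. In the same invented data, 350 patients are observed at week 24 and 365 are analysed under LOCF. The 41 with no post-baseline questionnaire stay out of both.

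**Size for DLQI 0/1.** Let p be the rate among those assessed, q the rate among those missing and m the missing share. The rate in all patients is p(1 − m) + qm, so the overstatement is m(p − q).

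| m | q | p = 50% | p = 60% | p = 80% |
|---|---|---|---|---|
| 41/406 (all leavers lack a questionnaire) | 0 | 5.0 points | 6.1 | 8.1 |
| 41/406 | p/2 | 2.5 | 3.0 | 4.0 |
| 20.5/406 (half of leavers) | 0 | 2.5 | 3.0 | 4.0 |
| 10.25/406 (a quarter) | 0 | 1.3 | 1.5 | 2.0 |
| any | p | 0 | 0 | 0 |

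In the first row, 50% becomes 0.50 × 365/406 = 45.0% and 80% becomes 0.80 × 365/406 = 71.9%. All rows assume that the percentage is taken over assessed patients. If the Safety-set N is the denominator, leavers already count as not achieving DLQI 0/1 and there is no gap.

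**Size for mean change.** If leavers had zero change, the observed mean is inflated by 1/(1 − m) = 406/365 = 1.11. An improvement of 10 points would be 9.0 in all patients.

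**The case against.** The strongest reply is that a reader might infer more than the documents support. Four parts of it stand.

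- **The duplication is not stated outright.** The rule removing patients with no post-baseline value (Protocol 9.4.3, SAP 2.7.3) is written for PASI. SAP 2.1.1.4 allows exceptions and governs only change scores. The identity is the natural reading for change and the paired tests, not a certainty.
- **DLQI 0/1 may not be affected.** It is a status at a visit, and its denominator is not given. Where the SAP does state denominators, it uses a full N: extension percentages in 1.1 and resource use in 2.11. Neither covers core-study DLQI, but an assessed-only denominator cannot be presumed.
- **The direction is not proven.** It is tempting to say that treatment failures are the ones removed. The only stop for non-response that the protocol mandates is at week 16 (5.5.9), a questionnaire visit, so those patients should be in the week-16 data. No document gives the reasons for leaving earlier.
- **The missing share may be well below 10%.** Protocol 6 asks patients who stop treatment to return for the Table 6-1 assessments, which include both questionnaires, and the wide window accepts early ones. The 10% is a sample-size allowance, not a forecast of missing questionnaires.

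It would also be wrong to call LOCF empty throughout, since it can differ from observed data from week 24 on.

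The reply does not rescue the text. If baseline is not carried, LOCF adds nothing to week-16 change; if it is carried, the rule is unwritten. A full-N denominator would settle the descriptive DLQI 0/1 rate, but not the change scores or the paired tests.

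**Conclusion.** The point holds in conditional form. Unless baseline is carried forward, week-16 LOCF repeats the observed-data analysis of DLQI and HADS change and the paired tests, and earlier leavers without a questionnaire are in neither. The week-16 results may then be overstated if those patients did worse; the documents do not establish that they did.

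For DLQI 0/1 the overstatement is 0 to about 5 points at an assumed observed rate of 50%, and 0 to about 8 points at 80%. The upper ends need all 41 allowed leavers to lack a questionnaire, none of them to have DLQI 0/1, and a denominator of assessed patients only. Mean improvement is inflated by at most about 11% if leavers are given zero change. At later visits LOCF differs from observed data, but patients with no post-baseline questionnaire remain excluded.

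**What to change.** In SAP 2.11:

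1. Add a non-responder analysis of DLQI 0/1 at each time point, with all Safety-set patients who have a baseline DLQI as the denominator. Use the existing rule and exceptions in SAP 2.5.3, including no imputation for extension patients who completed before week 72.
2. State whether baseline is carried forward for DLQI and HADS. If it is not, state that LOCF is not informative for change at week 16.
3. Reconcile the Safety set in 2.11 with ITT in 2.2 for these secondary objectives. This is a separate clarification and does not remove the problem above.

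A baseline-carried-forward or MMRM/multiple-imputation sensitivity analysis for change is optional. Baseline carry-forward has its own strong zero-change assumption, so it need not replace anything.

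The cost is SAP wording, a little more programming, and a DLQI 0/1 rate that may be less favourable.

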The cost for all items of assistance provided to the patient and included into the economic evaluation will be calculated according to price (such as for drugs) or tariffs (such as for tests).

For the costs attribution, since costs will not be collected in the CRF, an estimate for the following health services will be reported:

- drug treatment (ie. rescue medication)
- diagnostic services

In particular, for rescue medications (methotrexate, corticosteroids), cost will be assessed according to the dosage reported in the Patient Information Leaflets (PILs), considering an average price at the time of purchase.

Specialist services (Chest X-Ray, ECG, clinical chemistry tests, hematology tests, urinalysis) costs will be derived from regional tariffs and provided in a separate excel file (modified from http://salute.regione.emilia-romagna.it/documentazione/nomenclatore-tariffario-rer/nomenclatore_tariffario.xls/view); estimate costs for one month of rescue treatment will be reported in the same excel file.

Even though cost data are typically non-normally distributed (truncated at zero and positively skewed, reflecting the fact that some patients incur high costs), the arithmetic mean and standard deviation are the most informative measures in cost analysis.

These parametric methods are known to be fairly robust to non-normality, especially if the sample size is large, however robustness for a particular data set is difficult to judge.

All analyses will be performed considered the whole sample as denominator (ie. including those patients with a value equal to zero in a specific resource or in a specific cost item); for

example, for the number (and cost) of dermatological visits, the mean will be calculated as the sum of the dermatological visits in the whole sample divided by the number of subjects of the whole sample.

2.14 Interim analysis

No interim analysis is planned for this study.

3 Sample size calculation

The primary objective of this study is to evaluate the clinical response in PASI 90 at week 16 of Cw6-negative and Cw6-positive psoriatic patients. According to literature data, Cw6-positive patients will be about 60% of the entire psoriatic patient population.

From a previous study with ustekinumab (Talamonti et al. 2013) we can observe a difference in response to PASI 90 between Cw6-positive vs Cw6-negative patients of around 30%, in favor of Cw6-POS. Therefore, it is sensible to expect a response in the Cw6-negative cohort not less than 12 % respect to the Cw6-positive group. Further considerations are stated in the paragraph below.

Phase III data on secukinumab show a PASI 90 response at 16 weeks of 71%. Under the assumption that 60% of all the enrolled patient population is represented by Cw6-POS patients, we can reasonably assume to observe a proportion of patients with PASI 90 of 80% in the Cw6-POS cohort.

Under these assumptions, considering a one-side alpha level of 0.025 and a power of 80%, 365 patients (219 Cw6-POS and 146 Cw6-NEG) are sufficient to evaluate if the response in terms of PASI 90 in the Cw6-negative cohort is not less than 12% respect to the Cw6-positive cohort.

Considering a dropout rate at 16 weeks of 10% equally divided in the two studied cohorts, a total of 406 patients should be enrolled.

All calculations were done with NQuery 7.0.

A power analysis based on a different Cw6 patient distribution was made in order to facilitate patient enrollment without power-loss in the primary endpoint evaluation. Table 3-1 shows how the enrollment rate should be set free until the ratio between Cw6-POS and Cw6-NEG reaches the 1:1 rate-distribution, with a power of at least 80%.

In particular, the number of Cw6-POS evaluable patients will range from 219 to 182, whereas those in the Cw6-NEG cohort will range from 146 to 182.

Based on the table below, the enrollment in one of the two cohorts will be stopped when the target number is achieved (a maximum of 244 Cw6-POS patients will be allowed).

Table 3-1:Power analysis

Power	Ratio	Cw6	Cw6	Cw6	Cw6	Overall	Cw6	Cw6	

For business use only

		POS	POS	POS	POS		POS	POS
		%	%	Ν	Ν	Ν	%	%
80%	0.66	60%	40%	219	146	365	244	163
80%	0.70	59%	41%	215	150	365	239	167
80%	0.72	58%	42%	212	153	365	236	170
80%	0.75	57%	43%	209	156	365	233	174
81%	0.79	56%	44%	204	161	365	227	179
81%	0.82	55%	45%	200	165	365	223	184
81%	0.85	54%	46%	197	168	365	219	187
81%	0.89	53%	47%	193	172	365	215	192
81%	0.92	52%	48%	190	175	365	212	195
81%	0.96	51%	49%	186	179	365	207	199
81%	1.00	50%	50%	182	182	364	203	203

The choice of clinically relevant differences is based on the following considerations:

As the efficacy of secukinumab has already been clinically substantiated through extensive Phase II and III programs, all patients will be treated with active drug using the same therapeutic regimen (no placebo comparison will be done).

The primary variable is the proportion of patients who reach PASI 90 after 16 weeks. This endpoint is quite challenging and much more restrictive compared to PASI 75. Only the investigator is responsible for collecting the components or scoring signs and total regional areas in the PASI assessment. Therefore, it has great internal variability, which should be taken into account.

The paper on HLA-Cw6 ustekinumab data (Talamonti M et al. 2013) revealed a striking difference between Cw6-positive and Cw6-negative patients in the proportion of PASI 90 achievements, 85.7% vs 56.5%. This difference in PASI 90 is very relevant in the daily clinical management of patients.

Considering the above statements, it seems reasonable to claim that more than halving the difference observed with ustekinumab between Cw6-positive and Cw6-negative patients, secukinumab would be an advantage in terms of efficacy for Cw6-negative patients who do not respond properly to ustekinumab and other approved biologic drugs.

Although the sample size was calculated considering only Cw6 haplotype, it is also adequate for regression models assessing differences from baseline for clinically relevant variables. In fact, the expected number of patients who reach PASI 90 at week sixteen is at least 250 (roughly 71% of 365). Therefore, using a conservative criterion of a minimum of 10 "events" for each predictor in the model, we can add up to 25 variables in the model without loss of power (Vittinghoff E et al. 2007). This model will take into account variables such as BMI, smoking, metabolic syndrome and TNF α -308 polymorphism, which, among the six existing polymorphisms, is the one most greatly affecting response to treatment with anti-TNF α drugs.

4 Change to protocol specified analyses

The following changes and additions were done in different sections of the SAP.

General:

Summaries and analyses are extended based on 72 weeks duration.

Section 2.2 Analysis sets

Analysis Sets added for clarity or additional analyses:

- All patients: all patients who signed informed consent and entered in the study, including screen failure.
- Core phase completers set: All patients who completed the Core phase visits (Week 24) are called core phase completer set.

Analysis Sets updated/ clarified (in bold):

- Safety: all enrolled patients **included in the FAS population** who were given at least one dose of study drug.
- Intent-to-treat (ITT): all patients included in the safety population with at least one post-baseline efficacy assessment and with the Cw6 assessment.

Section 2.3.1:

By visit disposition summary table is added.

Section 2.3.2:

P-values of comparison of cohorts will be analysed based on stratified CMH, and logistic model with covariates (for categorical variables) and ANCOVA (for continuous variables).

Total number of comorbidities (all medical histories) between cohorts will be analyzed by Poisson model adjusted by covariates.

Section 2.4.2:

Previous psoriasis therapies will be analysed by logistic model and total number of such therapies will be analysed by Poisson model after adjusting for covariates.

Section 2.5:

The model factors are clarified in the SAP.

Non-responder imputation is added. Analyses based on NRI for primary and secondary efficacy endpoints are added.

Modelling approaches of PASI scores and IGA scores have been included based on MMRM. Modelling of IGA0/1 responder is also added.

Section 2.8.1

The AEs comparison of cohorts will be done based on CI and pvalues generated from logistic model or poisson model (for total number of events overall).

The AESI of RMP related events will be summarized and compared based on logistic model approach.

Section 2.8.4

ANCOVA model for vital signs are added.

5 Appendix

